7. DRUG FORMULATION AND ADMINISTRATION

7.1 Imprime PGG

7.1.1 Drug product formulation

Imprime PGG is supplied in 20-mL and 50-mL Type I clear borosilicate glass vials. Each vial contains PGG Beta Glucan at a nominal concentration of 1 mg/mL in a citrate-buffered saline solution (pH 5.0-7.5). Vials are filled to a target volume of 21.2 mL to ensure a deliverable amount of 20 mL per vial.

The active ingredient of the drug product is the beta glucan polymer, PGG Beta Glucan. The inactive ingredients of the drug product are sodium citrate and sodium chloride.

7.1.2 Storage

Imprime PGG should be stored between 15°C and 27°C.

7.1.3 Compatibility

Imprime PGG, is a sterile solution for IV. infusion. The appropriate dose based on body weight will be diluted by the site pharmacist in 0.9% Sodium Chloride so that the total volume of Imprime PGG and 0.9% Sodium Chloride equals the volumes specified below for strata of body weight in Section 7.1.6 Preparation and Route of Administration.

7.1.4 Handling

CONFIDENTIAL

This document is confidential. Do not disclose or use except as authorized.

Imprime PGG and rituximab for relapsed indolent NHL
November 13, 2018

Qualified personnel, familiar with procedures that minimize undue exposure to themselves and the environment, should undertake the preparation, handling, and safe disposal of the chemotherapeutic agent in a self-contained and protective environment.

7.1.5 Availability

Imprime PGG is an investigational agent and will be supplied free-of-charge from Biothera.

7.1.6 Preparation and Route of Administration

Imprime PGG, is a sterile solution for IV infusion. The appropriate dose based on body weight will be diluted by the site pharmacist in 0.9% Sodium Chloride so that the total volume of Imprime PGG and 0.9% Sodium Chloride equals the volumes specified below for strata of body weight.

Subject Weight in Kilograms	Imprime PGG Dose (mg/kg)	Total Infusion Volume (mLs)	Total Infusion Time (hours)	Rate of Infusion (mL/min)
≤75 kgs	4 mg/kg	500 mLs	2 hours (+/- 10 min)	4.2 mLs/min
>75 to ≤150kgs	4 mg/kg	750 mLs	3 hours (+/- 10 min)	4.2 mLs/min
>150 kgs	4 mg/kg	1000 mLs	4 hours (+/- 10 min)	4.2 mLs/min

The final volume will be administered by IV infusion at a rate of 4.2mL/min (total time to be determined by the total infusion volume) with a +/- 10 minute window. An infusion pump will be used to assure accurate and consistent dosing. Imprime PGG is supplied in 20-mL or 50-mL vials containing 20mg or 50mg, respectively, of Imprime PGG (1 mg/mL). The total storage time of Imprime PGG diluted in the IV bags, inclusive of administration, cannot exceed 8 hours at room temperature or 24 hours at 2-8⁰C.

7.1.8 Accountability

The investigator, or a responsible party designated by the investigator, must maintain a careful record of the inventory and disposition of the agent (investigational or free of charge) using the NCI Drug Accountability Record or another comparable drug accountability form. (See the CTEP website at <http://ctep.cancer.gov/protocolDevelopment> for the “Policy and Guidelines for

CONFIDENTIAL

This document is confidential. Do not disclose or use except as authorized.

Imprime PGG and rituximab for relapsed indolent NHL

November 13, 2018

Accountability and Storage of Investigational Agents” or to obtain a copy of the drug accountability form.)

7.1.9 Destruction and Return

At the end of the study, unused supplies of [agent] should be destroyed according to institutional policies. Destruction will be documented in the Drug Accountability Record Form.

7.2 Rituximab

7.2.1 Drug Product Information

Rituximab is commercially available and will be provided as an infusion prepared by a site pharmacist. Please refer to the FDA-approved package insert for rituximab for product information.

7.2.2 Storage

Intact vials should be stored under refrigeration. Dilute solutions for infusion (1-4 mg/mL) are stable for 24 hours under refrigeration, and for an additional 24 hours at room temperature.

7.2.3 Availability

Rituximab is commercially available in 10 mL and 50 mL single-use vials containing 100 or 500 mg of rituximab solution, respectively, at a concentration of 10 mg/mL. Please refer to the agent’s package insert for additional information.

7.2.4 Preparation and Route of Administration

The desired dose of rituximab should be diluted in 0.9% NaCl or D5W to a final concentration of 1-4 mg/mL. Mix by inverting the bag gently. Rituximab will be administered by IV infusion. Participants must be premedicated with hydrocortisone 100 mg IV, acetaminophen 650 mg, and diphenhydramine 25 mg PO, or their equivalents, prior to each dose. No specific prehydration is required.

CONFIDENTIAL

This document is confidential. Do not disclose or use except as authorized.

7.2.5 Destruction and Return

At the end of the study, unused supplies of [agent] should be destroyed according to institutional policies. Destruction will be documented and drug accountability for rituximab will not be documented since this drug will be charged to patients insurance.

8. CORRELATIVE/SPECIAL STUDIES

Participants will have one pretreatment peripheral blood sample collected within one week of starting treatment, 4 post-treatment peripheral blood samples collected approximately one hour following the completion of both infusions (one on each infusion day), and 3 pre-treatment blood samples collected at the time of routine lab collection on days 8, 15, and 22. Fresh whole blood samples will be processed in the laboratory of [name] and Biothera will provide the funding necessary to complete this work. Using reagents and a flow cytometric protocol provided by Biothera, we will quantify the percentage of Imprime PGG-bound and unbound neutrophils following each weekly treatment. Preclinical evaluation of healthy subjects, and cancer patients participating in Imprime PGG studies, demonstrate that based on the ability of Imprime PGG to bind to neutrophils and monocytes, subjects can be categorized into (i) binders- in which Imprime PGG bound to 5% or more of the total neutrophil population and (ii) low or non-binders- in which Imprime PGG bound to less than 5% of total neutrophils. We will correlate the percentage of Imprime PGG bound neutrophils with treatment response. Flow cytometric analysis of pre- and post-treatment changes in neutrophil activation marker expression using antibodies against CD11a, CD11b, CD63, CD87 and CBRM1/5 will also be performed.²⁵ This flow cytometric profile was used to quantify the proportion of activated neutrophils in whole blood before and after immunotherapy with an anti-tumor monoclonal antibody and GM-CSF in patients with neuroblastoma. All five markers of neutrophil activation were upregulated following treatment, and the degree to which they were upregulated correlated with outcome as reflected by progression-free survival. We will use this profile to quantify the proportion of activated neutrophils pre- and post-therapy on our study and correlate this with treatment response.

Finally, more recently it has been appreciated that one factor that distinguishes Imprime PGG “binders” from “non-binders” is whether a patients has a high level of endogenous anti-beta glucan antibodies. Preliminary clinical data indicate superior clinical response to beta-glucan therapy in biomarker positive (i.e. high binder, high anti-beta glucan level) patients (internal Biothera data). To investigate this further, Biothera has developed an in-house ELISA assay for the detection and quantification of IgG and IgM antibodies against beta glucan. Pre- and post-treatment serum samples obtained at the timepoints outlined above will be shipped to Biothera for analysis of anti-beta glucan antibody levels. Exploratory analysis of baseline beta glucan levels and binding capacity, and changes during therapy will be assessed and correlated with clinical outcomes.

CONFIDENTIAL

This document is confidential. Do not disclose or use except as authorized.

Imprime PGG and rituximab for relapsed indolent NHL
November 13, 2018

In the event that either funding and/or blood/serum samples are limited, these studies will be prioritized as follows: 1) flow cytometric analysis for quantification of Imprime PGG bound neutrophils 2) ELISA assay for detection and quantification of anti-beta glucan antibodies and 3) flow cytometric analysis for the quantification of activated neutrophils.

9. STUDY CALENDAR

Baseline evaluations are to be conducted within 2 weeks prior to the start of protocol therapy. Scans must be done ≤ 6 weeks prior to the start of therapy. In the event that the participant's condition is deteriorating, laboratory evaluations should be repeated within 48 hours prior to initiation of the next cycle of therapy.

All assessments must be performed prior to administration of any study medication. All study assessments and medications should be administered within ± 3 days of the protocol-specified date, unless otherwise noted.

The follow-up schedule will be at the discretion of the treating clinician, as long as the required study visits (see Table below) are met.

Study Calendar

Study Assessment	Baseline	Week 1	Week 2	Week 3	Week 4	Post Treatment⁶	Follow-up visits (6mo and 1 year +/- 4 weeks)⁴
Study Days	-14 to -1	1	8	15	22	92	
Study Drug: Imprime PGG		x	x	x	x		
Rituximab		x	x	x	x		
Medical History, Medication Review, Physical Exam, Weight	x	x	x	x	x	x	X ⁷
Toxicity Assessment		x	x	x	x	x	x

CONFIDENTIAL

This document is confidential. Do not disclose or use except as authorized.

Imprime PGG and rituximab for relapsed indolent NHL
November 13, 2018

ECOG Performance Status ¹	x	x	x	x	x	x	x
ECG	x						
CBC, Differential, Blood Chemistries ²	x	x	x	x	x	x	x
Hep B/C serology, pregnancy testing ⁸	x						
Tumor restaging ³	x ⁴					x ⁴	x ⁴
Peripheral blood collection for neutrophil studies ⁵	x ⁵						

¹Should be obtained at baseline and at the start of every cycle; see Appendix B for additional information.

²Blood chemistries to include complete metabolic panel, LDH. Labs on C1D1 do not have to re-meet eligibility other than the ANC must be >1000 as required for all treatment days.

³Tumor restaging will be with CT scans of the chest, abdomen, and pelvis.

⁴Tumor restaging should be performed within the 6 weeks prior to 1st administration of treatment, and 10 weeks +/- 3 days after week 4 of treatment. Surveillance during the one year +/- 4 weeks follow-up will include CT scans of the chest, abdomen and pelvis every 6 months from the end of treatment.

⁵ One pretreatment peripheral blood sample(s) will be collected for correlative studies (Section 8) within the 1 week prior to the first administration of treatment. Sampling will also be collected 1 hour following the end of both infusions and on each infusion day and pre-infusion with routine labs on days 8, 15, and 22 for all of the studies outlined in section 8.

⁶End of study visit to be performed 10 weeks +/- 3 days after the end of treatment with tumor restaging performed at this time.

CONFIDENTIAL

This document is confidential. Do not disclose or use except as authorized.

Imprime PGG and rituximab for relapsed indolent NHL

November 13, 2018

⁷At follow up visits, only medication review is required.

⁸Hepatitis B/C serology should include Hep B core, Hep B surface anti-body and antigen, Hep C anti-body, Hep B and Hep C viral loads.

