3.2 Exclusion Criteria

Participants who exhibit any of the following conditions at screening will not be eligible for admission into the study.

- 3.2.1 Patients currently receiving anticancer therapies or who have received anticancer therapies within 30 days of the start of study drug (including chemotherapy, radiation therapy, antibody based therapy, etc.). Steroids for symptom palliation are allowed, but must be either discontinued or on stable doses at the time of initiation of protocol therapy.
- 3.2.2 Patients may not be receiving any other investigational agents, or have received investigational agents within 4 weeks of beginning treatment.

CONFIDENTIAL

This document is confidential. Do not disclose or use except as authorized.

- 3.2.3 Patients who have previously received PGG-Betafectin (Betafectin®) or Imprime PGG.
- 3.2.4 Patients, who have had a major surgery or significant traumatic injury within 4 weeks of start of study drug, patients who have not recovered from the side effects of any major surgery (defined as requiring general anesthesia) or patients that may require major surgery during the course of the study.
- 3.2.5 Patients with known leptomeningeal or brain metastases. Imaging or spinal fluid analysis to exclude CNS involvement is not required, unless there is clinical suspicion by the treating investigator.
- 3.2.6 History of severe allergic or anaphylactic reactions to monoclonal antibody therapy or a known hypersensitivity to baker's yeast, unless in consultation with an allergy specialist they are deemed eligible for retreatment with desensitization.
- 3.2.7 Patients with known HIV infection or hepatitis B or C infection. HIV testing is not mandated and is to be performed at the discretion of the treating investigator.
- 3.2.8 Patients with a systemic fungal, bacterial, viral, or other infection not controlled (defined as exhibiting ongoing signs/symptoms related to the infection and without improvement, despite appropriate antibiotics or other treatment).
- 3.2.9 Prior history of another malignancy (except for non-melanoma skin cancer or *in situ* cervical or breast cancer) unless disease free for at least three years. Patients with prostate cancer are allowed if PSA is less than 1. Patients with indolent malignancies under control and which, in the opinion of the treating investigator, are unlikely to be clinically relevant or affect survival during the course of the study treatment and follow-up.

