9.1 Required data

The following must be obtained within 14 days prior to the 1st day of treatment:

- Medical history, medication review, physical exam, height and weight, ECOG performance status (see Appendix B)
- CBC with manual differential, blood chemistries including complete metabolic panel, LDH, quantitative immunoglobulins and β 2-microglobulin
- Hepatitis B and C serologies
- Serum or urine β -HCG for females of childbearing potential
- Electrocardiogram
- Tumor restaging (within 6 weeks). This will consist of CT scans of the chest, abdomen, and pelvis.
- Peripheral blood sample for neutrophil studies (within 1 week prior to the 1st of treatment; Section 8)

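### The only untreated neutrophil-activation sample may be drawn up to a week before dose 1, which can add avoidable between-day variation to the first-dose and from-baseline changes

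*Combined protocol and SAP*

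**What the plan says.** Three places set the time of the one sample that precedes all study drug, and they agree. Section 8 asks for "one pretreatment peripheral blood sample collected within one week of starting treatment". Footnote 5 of the Study Calendar says: "One pretreatment peripheral blood sample(s) will be collected for correlative studies (Section 8) within the 1 week prior to the first administration of treatment". Section 9.1 repeats the one-week window.

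For the later doses, Section 8 lists "3 pre-treatment blood samples collected at the time of routine lab collection on days 8, 15, and 22", and footnote 5 describes these as "pre-infusion with routine labs on days 8, 15, and 22 for all of the studies outlined in section 8". Neither list includes day 1. Post-dose samples are due about one hour after both infusions on all four infusion days, so dose 1 has a post-dose sample but no scheduled same-day partner.

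Section 8 plans to analyse changes from before to after treatment in five markers (CD11a, CD11b, CD63, CD87 and CBRM1/5), and then: "We will use this profile to quantify the proportion of activated neutrophils pre- and post-therapy on our study and correlate this with treatment response". Section 14.1 also names activated neutrophils as a correlative measure, but specifies no test.

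**The concern.** A pre-to-post change is easiest to interpret when both samples are close in time, so that little else moves between them. The schedule provides for this at doses 2 to 4 but does not require it at dose 1. Yet the dose 1 pre-sample is the only one taken before any study drug, so it is also the only untreated reference for a change from baseline.

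The documents leave room for real change in that week. On palliative steroids, Section 3.2.1 says: "Steroids for symptom palliation are allowed, but must be either discontinued or on stable doses at the time of initiation of protocol therapy". A patient could give the baseline sample while on steroids and stop before day 1. Blood is processed fresh, so a pair split across days is also split across assay days. Variation from either source would blur a correlation with response in a study of 25 patients.

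**Working it through.** No figure stated in the plan bears on this point, so the check compares the schedule across doses and then sizes the interval.

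**1. Schedule by dose**

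| Dose | Pre-dose sample | Post-dose sample |
|---|---|---|
| 1 (day 1) | any time in the preceding week | about 1 h after both infusions |
| 2, 3, 4 (days 8, 15, 22) | pre-infusion, with routine labs on those days | about 1 h after both infusions |

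Routine labs are also drawn on day 1 (calendar CBC row; Section 9.2), so a same-day draw needs no extra visit.

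**2. Length of the pre-to-post interval**

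Inputs from the documents:
- Imprime PGG infusion of 2 to 4 h, by body weight (Section 7.1.6).
- Minimum wait of 10 min (Section 5).
- Rituximab 375 mg/m². The first infusion runs at 50 mg/h for one hour, then rises by 50 mg/h every 30 min to at most 400 mg/h. Later infusions take 30 + 60 min (Section 5.2).
- Post-dose sample 1 h after both infusions (Section 8).

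Assumptions: body surface area 1.6 to 2.3 m², no interruption, and the pre-dose draw immediately before Imprime PGG.

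First rituximab infusion:
- 1.6 m²: 375 × 1.6 = 600 mg. By 3.5 h, 550 mg has been given; the last 50 mg at 350 mg/h takes 0.14 h. Total 3.64 h.
- 2.3 m²: 375 × 2.3 = 862.5 mg. By 4.0 h, 725 mg has been given; the last 137.5 mg at 400 mg/h takes 0.34 h. Total 4.34 h.

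Interval = Imprime PGG time + 0.17 h + rituximab time + 1 h:
- Dose 1, pre-sample on day 1: from 2 + 0.17 + 3.64 + 1 = 6.8 h to 4 + 0.17 + 4.34 + 1 = 9.5 h.
- Dose 1, pre-sample at the 7-day limit: add 168 h, giving 174.8 to 177.5 h. That is about 19 to 26 times as long (177.5/9.5 = 18.7; 174.8/6.8 = 25.7).
- Doses 2 to 4: from 2 + 0.17 + 1.5 + 1 = 4.7 h to 4 + 0.17 + 1.5 + 1 = 6.7 h.

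**3. What this could do to a correlation (illustration only)**

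The documents give no within-patient variance for the markers. Let k be the between-day variance divided by the variance of the same-day change, with the two parts independent. A true correlation ρ is then observed as ρ/√(1 + k). Approximate power, two-sided 5%, is Φ(atanh(r)·√(n − 3) − 1.96). Take ρ = 0.50 and n = 25, with every patient contributing a pair whose between-day variance is k:

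| k (assumed) | Observed r | Power |
|---|---|---|
| 0 | 0.50 | 73% |
| 0.1 | 0.48 | 68% |
| 0.25 | 0.45 | 62% |
| 0.5 | 0.41 | 53% |
| 1.0 | 0.35 | 41% |

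Both ρ and k are assumptions. Response is also binary, so this shows the direction and possible range of the loss and is not an estimate for this trial.

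**The case against.** The strongest reply is that the plan contains no error. The three places agree, and a draw on day 1 before infusion already satisfies the one-week wording. That is correct. A reader might infer that all 25 baselines will be a week old; the documents do not support this, because they set only a maximum and give no actual draw times. The single mark in the calendar's Baseline column does not settle it either, since its footnote also covers samples on later days. What stands is that the interval is uncontrolled and can differ between patients.

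Other stronger readings also fail:

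- **That a day 1 sample would isolate the effect of Imprime PGG.** Premedication that includes hydrocortisone (Section 5.3.1) and the full rituximab dose come between the two samples of every pair.
- **That same-day pairs would be guaranteed.** Section 5 allows rituximab to start up to 24 hours (+/- 4 hours) after Imprime PGG, and Section 5.2 lets an infusion finish the next day, so the post-dose sample may fall on day 2. The general ±3-day window in Section 9 also does not expressly rule out a separate lab day for the later pre-dose samples.
- **That growth factor would be given before dose 1 to reach the treatment-day neutrophil count.** Section 6.3.2 mentions growth factor for managing hematologic toxicity; no passage describes this earlier use.
- **That the first-dose change is the most informative of the four.** The protocol does not rank the pairs.

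The steroid route is permitted by the text, but the documents do not say how many patients use steroids or whether steroids alter these markers.

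It is also fair to say that little depends on this. The secondary objective in Section 1.3 names neutrophil binding, not activation. Section 8 puts activation last of three if funds or samples run short.

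**Conclusion.** The point holds as a low-cost improvement, not as a flaw in the main analysis. As written, the first-dose and from-baseline activation changes can carry up to 7 days of between-day biological and assay variation, to a degree that differs by patient. The later pairs largely avoid this. The interval can be about 175 to 178 hours, against about 7 to 9.5 hours with a day 1 draw, under the infusion assumptions stated. The resulting loss of precision cannot be computed from the documents.

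The consequence is confined to the exploratory activation correlate. ORR, PFS and safety do not use this sample. The bound-neutrophil percentage is measured after each weekly treatment, so the 5% binder classification does not depend on the pre-dose pair.

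**What to change.** In Section 8, Section 9.1 and footnote 5:

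- Schedule the pretreatment correlative sample on day 1 with the routine week 1 labs, before premedication and Imprime PGG, matching days 8, 15 and 22.
- Process it on the same day as the post-infusion sample where both infusions finish that day.
- Accept a screening-week sample only as a fallback.
- Record all draw times and flag any pair not drawn on the same day, so that the activation analysis can be repeated without those pairs.

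This changes one timing phrase in three places and adds a flag to the data. It needs no extra visit or assay. The downside is a redraw if day 1 treatment is postponed. Serum for the anti-beta glucan antibody assay is taken at the same time points, so the revised wording should say whether that draw moves as well.

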9.1 Required data

The following must be obtained within 14 days prior to the 1st day of treatment:

- Medical history, medication review, physical exam, height and weight, ECOG performance status (see Appendix B)
- CBC with manual differential, blood chemistries including complete metabolic panel, LDH, quantitative immunoglobulins and β 2-microglobulin
- Hepatitis B and C serologies
- Serum or urine β -HCG for females of childbearing potential
- Electrocardiogram
- Tumor restaging (within 6 weeks). This will consist of CT scans of the chest, abdomen, and pelvis.
- Peripheral blood sample for neutrophil studies (within 1 week prior to the 1st of treatment; Section 8)

9.2 Required data during study

The following must be obtained during the study:

- Medical history, medication review, physical exam, and weight, ECOG performance status (see Appendix B)
- Toxicity assessment
- CBC with manual differential, blood chemistries including complete metabolic panel and LDH – day 1 of week 1-4
- Peripheral blood sample for neutrophil studies 1 hour after treatment on day 1 of weeks 1-4 of treatment and serum for evaluation of anti-beta glucan antibody levels

9.3 Required at post-treatment visit (10 weeks +/- 3 days from end of treatment)

The following must be obtained at post-treatment visit (10 weeks +/- 3 days from the last day of treatment).

CONFIDENTIAL

This document is confidential. Do not disclose or use except as authorized.

- Medical history, medication review, physical exam, height and weight, ECOG performance status (see Appendix B)
- Toxicity assessment
- CBC with manual differential, blood chemistries including complete metabolic panel and LDH
- Tumor restaging, which will consist of CT scans of the chest, abdomen, and pelvis
- Surveillance during the six month and 1 year (+/- 4 weeks) follow-up period (from the end of treatment) will include physician visits with routine laboratory evaluation, physical exam, and CT scans of the chest, abdomen, and pelvis every 6 months. Additional physician visits with routine laboratory assessment and physical exam will be left up to the discretion of the treating physician.

